55-74). There were 297 individuals who were reachable and 54 of these were eligible for LCS according to the USPSTF criteria. We were able to contact a higher proportion of current smokers (47%) than former smokers (30%). Eligibility was higher in current smokers (28%) versus former smokers (11%). Also, of the 54 total eligible, 28 enrolled. Despite these small numbers, we were able to show the DCP participation was associated with LDCT completion at 90 days ($p=0.03$).

Study Design We propose a 1 year project including a **6 month intervention** period. This study will be a cohort with comparison to usual care in other practices in the same health system using propensity-matching methodology. **Study population/eligibility** Inclusion/exclusion criteria will be based on the USPSTF and CMS lung cancer screening guidelines: age 55- 80, with a 30 pack year smoking history, no symptoms consistent with cancer, and no CT scan of the lungs within the last year. Physicians will be given the chance to eliminate participants based on limited life expectancy or prohibitive comorbid conditions. Case finding in our prior work was difficult and recruiting active smokers has a higher yield. Prior work indicated that this pool yielded a higher proportion of truly eligible, reachable individuals. Plus, we want to test the feasibility of a more intense smoking cessation intervention. To address recruitment barriers, we will work with practices and PCPs to promote as a study “conducted with the PCP,” including the physician name or practice name when possible on recruitment materials e.g. written letters and email cosigned by their PCP. To address case finding barriers, we will allow patients to easily opt out of future contact via mail, email or phone. We will work with our advisory panel to explore other methods to enhance recruitment and case-finding such as using the secure EMR portal to screen for LCS eligibility and/or updating smoking history. Finally, we have added \$50 patient incentives per patient for participation.

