Intervention The DCP is an online software application that supports an interactive session that focuses on patient education and preference clarification. Patients will be contacted by phone or other methods to provide information about the study, be invited to participate, consented, and then scheduled for decision counseling. Neither the DCP tool nor this process is directive; the DCP session does not push the patient to screen but, rather, clarifies the patient's current preference (screen or not) and identifies key reasons for that preference. In the session, the decision counselor and patient will review the options, (to screen or not to screen for lung cancer) using publicly available patient education materials (Appendices 1 & 2) (8, 9). Then, the decision counselor will guide the patient through 5 steps: 1) identify factors most likely to influence the decision to screen 2) assign importance (decision weight) to the factors 3) compare the relative weight of the most important factors 4) generate a decision score, and 5) generate a personal summary form which can be made available in the EMR for physician review with the patient. Next steps will be tailored to each practice, and can include referral to PCP for further discussion and/or referral to the Lung Health Screening Program (LHSP). The decision counselor will be trained as a smoking cessation coach and as a “mini-expert” in system and community resources for smoking cessation.

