Data Acquisition Following approval by the CCHS Institutional Review board, lists of potentially eligible individuals from participating and non-participating practices will be obtained from EMR data. These lists will be automatically entered into a REDCap® for CONSORT tracking. Lists will be organized according to PCP whom will be given 7 working days to review lists and eliminate any patient they feel would not be appropriate for this study. Remaining potentially eligible patients will receive a letter, cosigned by their personal physician which introduces the study and offers the opportunity to easily opt out of further contact. After an opt-out period of 7 working days, patients will be contacted, screened for eligibility and invited to participate. After formal consent, we will collect demographics, socioeconomic variables and smoking history. Baseline data will be collected regarding knowledge, preference and decisional conflict related to lung cancer screening. Standard patient education materials will be sent to patients. The DCP session will be conducted within 30 days of enrollment. A follow up telephone call will occur within 30 days of DCP completion, and will include items to assess patient perception of the process, knowledge about lung cancer screening and decisional conflict (Appendix 3) related to lung cancer screening (10). At 60 days after the decision counseling session, patient charts/electronic medical record data will be audited for the primary outcome, LDCT scan report. Prior work showed the average time from DCP to LDCT was ≤ 60 days. Intermediate (process) outcomes in EMR include lung cancer screening discussion, referral/order for LDCT, or referral to the CCHS LHSP. Eligible patients in the usual care group (in the non-participating clinics) will be identified electronically as stated above and LDCT screening assessed in a 60 day study period from their most recent office visit. Information available in EMR for all patients including controls and individuals who are “unreachable” comprises gender, age, race, ethnicity, insurance status, marital status, smoking status, comorbidities, such as COPD, Heart disease, diabetes, hypertension and zip code (surrogate for socioeconomic status). Information collected from individuals who are reached but ineligible will include all of the above plus smoking status, pack years, and reason for ineligibility. Information collected from individuals who decline participation will include all of the above plus reason for declining participation.

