
Statistical analysis

Aim 1 Compare low dose CT scan completion in the DCP cohort of current smokers versus usual care propensity-matched controls at 60 days. *Hypothesis: Participation in the DCP will be associated increased participation in LDCT, compared with both eligible enrollees who do not participate and with eligible patients in usual care practices.* Demographic and clinical variables of the intervention and control groups will be compared using T-Test, Wilcoxon-Rank sum test and chi-squares. We will conduct a 1-to-1 propensity score matching to compare the proportion of patients who screen between the groups. We will use a logistic regression model to build propensity scores to match patients in the intervention and control groups. We will model the probability of being in the intervention group using all the patients level variables extracted from the medical records as listed above. Whether they are in a participating practice or not will not be included in the model as an independent variable. The nearest neighborhood method without replacement will be used for matching. We will set the caliper width according to the standard deviation for the propensity score. Each control will be assigned a probability score and matched with a patient in the intervention group. In a second step, we will compare the characteristics of the patients and chosen controls to verify that they are very similar. We will use a simple chi-square to compare the percentage of patients in the control and intervention groups who complete the LDCT scan within 60 days.

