Power calculation based on primary outcome: According to our preliminary study, 45% of those who complete the DCP decided to screen for lung cancer whereas the know rate of screening among patients in usual care is 15%, which makes a difference of 30%. A sample size of 40 patients in each group will achieve 85% power to detect a difference between the group proportions of 30%. The proportion in the intervention group is assumed to be 15% under the null hypothesis and 45% under the alternative hypothesis. To detect a difference of 20%, we will need a sample size of 60 patients in each group to achieve a power of 80%. We expect that 2000 patients will be identified as potentially eligible for the study in the EMR and 1000 will be reachable. Of those 300 (30%) will be confirmed eligible during the phone call and 150 (50%) will accept to participate in the DCP. We will therefore have ample power to detect a difference as small as 20% between our 2 groups.

Aim 2 Compare the characteristics of the patients not recruited in the study to the characteristics of those who accepted to enroll. *Hypothesis: Patients recruited to the study versus those who are not will be different demographically and geographically.* We will use descriptive statistics to examine the characteristics of the patients of the intervention practices who were eligible but could not be reached and of the patients who were reached but refused to be in the study. We will also compare the characteristics of these patients to those of the patients who enrolled in the study. We will use logistic regression models to determine which independent characteristics are associated with agreeing to be in the study.

Aim 3 Test the feasibility of intensive smoking cessation as part of the DCP. *This aim is hypothesis generating.* At 30 days, we will ask patients about participation in smoking cessation, quit attempts and for general comments on their needs and satisfaction with our smoking cessation efforts. We will explore trends associated with these intermediate outcomes related to cessation including engaging in cessation and quit attempts. We will illicit qualitative information from participants about how to make this part of the program useful and patient-centered.

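### Does the stated power fail to apply to the 60-day LDCT endpoint because its 45% is described as a decision to screen?

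*Combined protocol and SAP*

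**What the plan says.** The paragraph on power in the Statistical analysis section (Aim 1) states that, in the preliminary study, "45% of those who complete the DCP decided to screen for lung cancer", and that "the know rate of screening among patients in usual care is 15" percent. It obtains 85% power with 40 patients per group for that 30-point difference. It then gives 60 per group for 80% power at a 20-point difference, expects 150 patients to accept, and concludes that power is ample for a difference as small as 20 points. Specific Aims plans to recruit 100.

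The endpoint is defined in Data Acquisition: "At 60 days after the decision counseling session, patient charts/electronic medical record data will be audited for the primary outcome, LDCT scan report". For usual care it is "LDCT screening assessed in a 60 day study period from their most recent office visit". Under Aim 1 the test is a chi-square to "compare the percentage of patients in the control and intervention groups who complete the LDCT scan within 60 days".

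Three other statements bear on the inputs:

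- Intervention: the session clarifies the patient's "current preference (screen or not) and identifies key reasons for that preference".
- Preliminary Studies: "we were able to show the DCP participation was associated with LDCT completion at 90 days", with p=0.03 but no proportion; 28 of the 54 eligible patients enrolled.
- Data Acquisition: "Prior work showed the average time from DCP to LDCT was ≤ 60 days".

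**The concern.** Read literally, the 45% counts people who made up their minds to be screened, and the endpoint counts people with a scan report. The plan itself keeps these apart: the session yields a preference, and a discussion, an order or a referral are listed as intermediate outcomes. Some people who decide to be screened will not have been scanned by day 60.

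Nothing else in the document supplies the missing rate. The pilot's completion result is at 90 days and has no percentage. A mean time to scan of at most 60 days describes only those who were scanned, and a mean does not give the share scanned by day 60. The 15% has neither a window nor a source.

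If the true 60-day rate in the DCP group were well below 45%, the quoted 85% would overstate power, and 40 per group leaves almost no slack. A null result might then reflect an undersized comparison, and a mislabelled effect size could carry over into the randomized trial that this work is meant to prepare.

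**Working it through.** **Inputs.** From the document: rates of 15% and 45%, 40 per group, 1-to-1 matching, a 20-point second scenario, and 100 (planned) or 150 (expected) participants. Assumed, because not stated: two-sided alpha of 0.05, uncorrected test, equal groups, every participant matched.

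**Formula.** With p̄ = (p₁+p₂)/2,

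Power = Φ( [ |p₂−p₁| − 1.96·√(2p̄(1−p̄)/n) ] / √( [p₁(1−p₁)+p₂(1−p₂)]/n ) ).

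**Step 1: the plan's own figure.** For 15% v 45% at n = 40, p̄ = 0.30. The null standard error is √(2×0.30×0.70/40) = 0.1025. The alternative standard error is √((0.1275+0.2475)/40) = 0.0968. Then (0.30 − 1.96×0.1025)/0.0968 = 1.02, and Φ(1.02) = 84.7%. The stated 85% reproduces.

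**Step 2: vary what the inputs might be.** The document gives no 60-day rate for either group, so these pairs are illustrations.

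| Usual care v DCP | 40 per group | 100 per group | 150 per group |
|---|---|---|---|
| 15% v 45% (as stated) | 85% | 99.8% | >99.9% |
| 15% v 40.5% (90% of 45%) | 73% | 98% | 99.9% |
| 15% v 36% (80% of 45%) | 58% | 93% | 99% |
| 15% v 35% (the plan's 20 points) | 54% | 91% | 98% |
| 15% v 31.5% (70% of 45%) | 41% | 79% | 93% |
| 15% v 30% | 36% | 72% | 88% |
| 10% v 30% (both cut by a third) | 61% | 95% | 99% |
| 5% v 30% | 85% | 99.8% | >99.9% |

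**Step 3: break-even for 80% power.**

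- Usual care fixed at 15%: the DCP rate must be at least 43.0% at 40 per group, 31.7% at 100 and 28.3% at 150. Divided by 45%, that is 96%, 70% and 63% of the stated rate.
- Both rates scaled by the same factor: 80% power survives down to a factor of 0.92 at 40 per group, 0.45 at 100 and 0.31 at 150.

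**Step 4: the effect size behind the conclusion.** The closing claim concerns 20 points. With usual care at 15% that means a DCP rate of 35%, which is 35/45 = 78% of the pilot figure. The plan therefore already allows for a 22% shortfall. For 15% v 35%, 73 pairs give 80% power, so 100 or 150 participants leave room for 27 or 77 to go unmatched.

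**The case for a change.** The strongest case for acting is that the correction is almost free and the text does not say what the numbers are. Even if deciding to screen means having been screened, the only pilot completion window mentioned is 90 days, so the 60-day rate is still not shown. If one in ten of the 45% had no scan by day 60, power at 40 per group drops to 73%. At 100 pairs it falls below 80% once the DCP rate is under 31.7%. Caliper matching may also leave fewer pairs than patients recruited.

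What stands is narrow: the two inputs lack an event definition, window, denominator and source. The rest carries less weight.

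- **Wording.** The paragraph is presented as concerning the primary outcome, and the same sentence subtracts a usual-care screening rate from the 45%. That fits a completion rate better than a recorded preference. The text cannot settle it.
- **Direction.** Holding usual care at 15% while cutting the DCP rate shows only the unfavourable half. The 15% has no window either. If it covers more than 60 days, the 60-day control rate is lower and power recovers: 5% v 30% gives the stated 85% even at 40 per group. The only other screening rates in the document, 3.3% and 3.9% nationally, are not 60-day rates in this health system, but they give no reason to fix controls at 15%.
- **Size.** Forty per group is not the number the study plans to stop at.
- **Precision.** A 60-day rate from at most 28 pilot enrollees would be imprecise, so it would not replace 45% with a firm value.

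One neighbouring figure does not reproduce: 60 per group for 15% v 35% gives 72% on the two-sided basis that yields the 85%, and 73 per group would be needed for 80%. That is a separate matter. It does not alter this point, because both 100 and 150 exceed 73.

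**Conclusion.** The mismatch in wording is real, but it does not call for a change. It is a gap in documentation, and whoever holds the pilot data can fill it by noting the event, window, numerator and denominator behind the 45% and the source of the 15%. Endpoint, follow-up, test and sample size would all stay the same.

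At the planned 100 to 150 per group, the plan's own 20-point difference keeps 91% to 98% power. The exposed case is a DCP rate below about 70% of the pilot figure with no fall in usual care: 15% v 30% gives 72% at 100 pairs, though 88% at 150. Nothing in the document shows that this case applies.

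The conclusion assumes a two-sided 5% uncorrected test, equal groups, and matched pairs close in number to the patients enrolled. If matching left far fewer than about 73 pairs, the margin on the 20-point difference would be gone, whichever event the 45% describes.

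### The two power statements conflict: at a 15% usual-care rate, 60 per group gives about 72% power for a 20-point difference, not 80%

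*Combined protocol and SAP*

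**What the plan says.** The paragraph on power for the primary outcome (Statistical analysis, Aim 1) takes two rates as its starting point. For usual care, "the know rate of screening among patients in usual care is 15" per cent. From the preliminary study, "45% of those who complete the DCP decided to screen for lung cancer". It then makes two statements:

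- **30 points:** "A sample size of 40 patients in each group will achieve 85% power to detect a difference between the group proportions of 30" per cent, with the rates spelled out: "The proportion in the intervention group is assumed to be 15% under the null hypothesis and 45% under the alternative hypothesis".
- **20 points:** "To detect a difference of 20%, we will need a sample size of 60 patients in each group to achieve a power of 80" per cent. The two rates behind this difference are not given.

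The paragraph expects 150 participants and concludes: "We will therefore have ample power to detect a difference as small as 20% between our 2 groups". The Specific Aims section gives 100 recruits instead.

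Under Aim 1, matching is 1-to-1 without replacement and with a caliper ("We will set the caliper width according to the standard deviation for the propensity score"). The test is uncorrected as described: "We will use a simple chi-square to compare the percentage of patients in the control and intervention groups". No alpha and no sidedness appear anywhere in the document.

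**The concern.** Both statements concern the same test, outcome and usual-care rate, so one alpha should reproduce both. With the effect cut from 30 to 20 points, an increase from 40 to only 60 per group looks too small. The required number scales roughly with the inverse square of the difference, a factor of (30/20)² = 2.25, before allowing for the change in variance and for the lower power target.

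If 60 is too low, a reader could accept 60 to 72 matched pairs as enough for the 20-point scenario when power is below 80%. The Sustainability section describes the pilot as preparation for a randomized trial, so the same figure could also be carried into that trial's planning.

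**Working it through.** **Inputs from the document.** Usual-care rate p1 = 0.15. Intervention rate p2 = 0.45 for the 30-point scenario. Groups of 40 and 60. Chi-square test, 1:1.

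**Assumptions.** Two-sided alpha 0.05 (critical value 1.960), chosen because it reproduces the first statement. For the 20-point scenario p1 stays at 0.15, so p2 = 0.35.

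**Formula.** With d = p2 − p1 and p̄ = (p1 + p2)/2:

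- SE0 = √[2p̄(1 − p̄)/n]
- SE1 = √{[p1(1 − p1) + p2(1 − p2)]/n}
- power = Φ[(d − z·SE0)/SE1]

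**Step 1: the 40-per-group statement.** p̄ = 0.30, SE0 = 0.1025, SE1 = 0.0968. (0.30 − 1.960 × 0.1025)/0.0968 = 1.024, so power is **84.7%**. This matches the stated 85%.

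**Step 2: the 60-per-group statement, same assumptions.** p̄ = 0.25, SE0 = 0.0791, SE1 = 0.0769. (0.20 − 1.960 × 0.0791)/0.0769 = 0.586, so power is **72.1%**. The stated figure is 80%.

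**Step 3: number needed for 80%.** n = {[1.960·√(2 × 0.25 × 0.75) + 0.842·√(0.15 × 0.85 + 0.35 × 0.65)]/0.20}² = (1.7017/0.20)² = 72.4, so **73 per group**. At 60 per group, the smallest difference from 15% with 80% power is about 22.3 points.

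| Pairs | Power, 15% vs 35% |
|---|---|
| 60 | 72.1% |
| 65 | 75.5% |
| 70 | 78.6% |
| 72 | 79.8% |
| 73 | 80.3% |
| 100 | 91.0% |
| 150 | 98.2% |

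**Step 4: does another alpha or method fit both statements?**

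| Method | 40 per group, 30 points (stated 85%) | 60 per group, 20 points (stated 80%) |
|---|---|---|
| Pooled, two-sided 0.05 | 84.7% | 72.1% |
| Unpooled, two-sided 0.05 | 87.3% | 73.9% |
| Arcsine, two-sided 0.05 | 85.5% | 73.2% |
| Exact enumeration of uncorrected chi-square, two-sided 0.05 | 85.2% | 73.5% |
| Continuity-corrected pooled, two-sided 0.05 | 77.8% | 64.4% |
| Fisher, two-sided 0.05 | 79.3% | 65.2% |
| Pooled, one-sided 0.05 | 91.3% | 81.8% |
| Exact enumeration of uncorrected chi-square, one-sided 0.05 | 92.1% | 82.9% |
| Continuity-corrected pooled, one-sided 0.05 | 86.4% | 75.6% |
| Fisher, one-sided 0.05 | 87.5% | 76.5% |

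No row gives 85% and 80% together. Solving the pooled formula for two-sided alpha gives the same answer: 85% at 40 per group needs alpha 0.051, which gives 72.5% at 60. 80% at 60 per group needs alpha 0.087, which gives 90.1% at 40.

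**Step 5: other base rates for the 20 points.** Counting down from the 45% intervention rate (25% vs 45%) gives 63.5% at 60 per group and needs 89 per group for 80%. Holding two-sided 0.05 and the pooled formula, 80% at 60 per group requires a usual-care rate of about 9%.

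**The case against.** **The base rate.** The 20-point sentence does not give its rates, so 15% vs 35% is supplied by the reader. If the authors used 10% vs 30%, 60 per group gives 78.9% by the pooled formula and 80.2% by exact enumeration of the uncorrected chi-square. That exact test also gives 85.2% for the first statement, so one test at two-sided 0.05 would reproduce both. This is arithmetically right. However, 15% is the only usual-care rate in the power paragraph and is presented there as known. If a lower rate was used, the sentence still needs correcting, because it then rests on an unstated rate that differs from the one given.

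**Practical effect.** Nothing in the document uses 60 as a recruitment target or stopping point, and planned enrolment is well above 73. This stands and limits the point's importance. The pairs fall below 73 only if matching loses more than 27 of 100 participants (100 − 73) or more than 77 of 150 (150 − 73). With no stated match rate, the chance of that cannot be judged. Re-use of the figure in a later trial is possible but not stated.

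**The figure of 73.** It belongs to the pooled formula. Exact enumeration of the uncorrected chi-square first reaches 80% at 71, and a continuity correction asks for 83. The formula also treats the groups as independent and ignores any within-pair correlation, as the planned chi-square does. So 73 should be quoted with its formula and alpha. None of these variants brings the requirement down to 60.

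**Conclusion.** The concern holds. With the plan's 15% usual-care rate and one test at one alpha, no method tried reproduces both power statements. Under two-sided 0.05, which reproduces the first, power at 60 per group for 15% vs 35% is 72.1% (72% to 74% across the two-sided 0.05 methods that come near the stated 85%). The number needed for 80% is 73 per group, 13 more than stated (13/60 = 22%).

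The result rests on two assumptions: that the 20 points are counted up from 15%, and that both statements share an alpha. The conclusion of ample power survives at 100 or 150 pairs. This is an error in a stated figure that should be corrected. It does not show that the study is underpowered.

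**What to change.** State alpha, sidedness, the formula and both rates for the 20-point scenario. If two-sided 0.05 and the 15% rate were intended, replace the sentence with:

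> To detect 15% versus 35% (two-sided alpha 0.05, pooled chi-square), 73 matched pairs give 80% power; 60 pairs give 72%. The 20-point claim holds provided at least 73 pairs remain after caliper matching (power about 91% at 100 pairs and 98% at 150).

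If one-sided 0.05 was intended, say so and correct the other figure: 40 per group then gives about 91%, not 85%. If the 20-point scenario used a lower usual-care rate, state that rate and justify it against the 15% given in the same paragraph.

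The cost is a text correction of one or two sentences, with no extra patients and no change to design or analysis.

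### Aim 2 compares phone-confirmed enrollees with unreached patients whose eligibility is unconfirmed, so that contrast mixes eligibility with reach and consent

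*Combined protocol and SAP*

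**What the plan says.** Statistical analysis, Aim 2, names two non-recruited groups: "the patients of the intervention practices who were eligible but could not be reached", and those who were reached but refused. Both are to be described and compared with enrollees. Logistic regression will then look for characteristics associated with agreeing; the patients who enter that model are not stated.

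Eligibility is settled only on contact. Under Approach, Data Acquisition, after physician review of the list and a letter with an opt-out, "patients will be contacted, screened for eligibility and invited to participate". The power calculation gives the expected flow: "We expect that 2000 patients will be identified as potentially eligible for the study in the EMR and 1000 will be reachable". It continues: "Of those 300 (30%) will be confirmed eligible during the phone call". Half of these, 150, are expected to accept.

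The criteria under Study population/eligibility combine age 55 to 80 "with a 30 pack year smoking history, no symptoms consistent with cancer, and no CT scan of the lungs within the last year". The EMR information for all patients, including the unreachable, "comprises gender, age, race, ethnicity, insurance status, marital status, smoking status, comorbidities, such as COPD, Heart disease, diabetes, hypertension and zip code". Pack-years are added for people who are reached but ineligible and for decliners, together with the reason for ineligibility or for declining. The lists go into a database "for CONSORT tracking". One idea for better case-finding, "using the secure EMR portal to screen for LCS eligibility and/or updating smoking history", is only to be explored with the advisory panel.

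**The concern.** The two sides of the enrolled-versus-unreached contrast are not filtered in the same way. Enrollees have been reached, confirmed eligible and consented. The unreached have only been listed. The reached-but-ineligible patients belong to neither non-recruited group, so ineligible patients leave the reached side and stay in the unreached side.

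Aim 2 expects recruited and non-recruited patients to differ demographically and geographically. A trait that is simply more common among people who meet the pack-year criterion would appear as such a difference, under a label that says both groups were eligible. It could then be read as a problem of contact or of willingness. Better case-finding, better contact methods and better invitations are different remedies, so the reading matters when the later randomised trial is planned.

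**Working it through.** **Inputs from the plan.** Power calculation: 2000 listed, 1000 reachable, 30% of those confirmed eligible, 50% of those accepting. Preliminary Studies: 28% of current smokers eligible. Specific Aims: recruitment target of 100.

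**Plan's own figures, reproduced.** 0.30 × 1000 = 300 confirmed eligible; 0.50 × 300 = 150 enrolled. Hence 300 − 150 = 150 declining, 1000 − 300 = 700 reached but ineligible, and 2000 − 1000 = 1000 not reached. The last figure may include physician-removed and opt-out patients, whose number is not given.

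**Ineligible share of the unreached.** Let e be their eligible share. No figure is given, so the rate in the reached is carried over as an assumption.

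- e = 0.30: 1000 × (1 − 0.30) = 700 ineligible.
- e = 0.28: 1000 × (1 − 0.28) = 720 ineligible.

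**Gap from eligibility alone.** Let a trait have prevalence pE in eligible and pI in ineligible patients, with D = pE − pI, and let it be unrelated to reach and consent. Enrollees show pE and the unreached show e·pE + (1 − e)·pI. The gap is pE − [e·pE + (1 − e)·pI] = (1 − e)·D. D is not in the documents; the values below are assumed, as are e = 0.50 and e = 0.20. Entries are percentage points.

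| e | D = 5 | D = 10 | D = 20 |
|---|---|---|---|
| 0.50 | 2.5 | 5.0 | 10.0 |
| 0.30 | 3.5 | 7.0 | 14.0 |
| 0.28 | 3.6 | 7.2 | 14.4 |
| 0.20 | 4.0 | 8.0 | 16.0 |

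**Sampling error for scale.** The 95% half-width is 1.96·√[p(1 − p)(1/n1 + 1/n2)], with p = 0.30 assumed.

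- Enrolled vs unreached, 150 vs 1000: ±7.9 points.
- Reached vs unreached, 1000 vs 1000: ±4.0; with an assumed 500 unreached, ±4.9.
- Confirmed eligible vs ineligible among those screened, 300 vs 700: ±6.2.
- Enrolled vs declined, 150 vs 150: ±10.4.
- Enrolled vs declined, 100 vs 100 (the target of 100 at 50% acceptance): ±12.7.

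The first two contrasts estimate different quantities, so the narrower interval for reached versus unreached is not a gain in precision on the same question.

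**The case against.** - **The label follows the plan's own usage.** Data Acquisition also calls usual-care patients eligible when they are identified electronically, so the word in Aim 2 may mean no more than EMR-eligible. That answers the label. It leaves the comparison with phone-confirmed enrollees as it was.
- **Physicians review the list first.** They do, but before contact, and the plan still expects only 30% of those reached to be confirmed.
- **The affected part is mainly descriptive.** The one model named concerns agreeing, which presupposes being asked, and patients are invited only after screening. This stands in large part. It limits the point to one contrast and, for the model, to an unstated analysis set.
- **The size is assumed.** At 70% ineligible, the gap exceeds the ±7.9-point half-width only if D is above 7.9/0.70 = 11.3 points. Nothing in the documents shows a D that large for demographic or geographic traits. This stands.
- **A stepwise analysis has limits of its own.** Comparing everyone reached with everyone not reached describes the whole list, most of it probably ineligible. It is free of the eligibility artefact only if the eligible share is similar on both sides. In the pilot, contact (47% vs 30%) and eligibility (28% vs 11%) were both higher in current than in former smokers, so reach and eligibility need not be independent. Restricting recruitment to current smokers lessens this but does not prove equality. These conditions belong in the plan.

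**Conclusion.** The point holds for the enrolled-versus-unreached contrast. As planned, that group is potentially eligible and not reached, and its comparison with enrollees combines eligibility, reach and consent. If the 30% confirmation rate carries over to the unreached, about 700 of 1000 are ineligible, and eligibility alone would produce a gap of about 0.7D. Both that rate and D are assumptions.

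Three stronger readings are tempting, and the documents do not support them:

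- **That Aim 2 will be seriously biased.** D is unknown, so the distortion may be negligible or material.
- **That all of Aim 2 fails.** Enrolled versus refused among screened patients is unaffected, and so is a logistic model confined to them.
- **That Aim 1 is thereby cleared or undermined.** This point makes no statement about how eligibility is confirmed in the Aim 1 controls.

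This is a low-priority point on a secondary aim of a pilot, worth correcting because the correction needs no new data.

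**What to change.** Relabel the group as EMR-listed (potentially eligible), not reached, and analyse Aim 2 by step, using the tracking and data already planned:

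1. **Reach.** All reached patients, eligible or not, versus not reached, among listed patients for whom contact was attempted. State that this describes reach in the whole EMR list, may dilute a reach difference confined to eligible patients, and avoids the eligibility artefact only if the eligible share is similar in both groups.
2. **Eligibility.** Confirmed eligible versus ineligible among those screened, as a guide to D. State that it applies to reached patients only; using it for the unreached is an assumption. At about ±6 points it will not resolve a small D.
3. **Consent.** Enrolled versus declined among the confirmed eligible, with the logistic model for agreeing fitted only there.

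Tabulate separately the patients removed by physicians, those who opted out by letter, and those who refused before screening. A direct enrolled-versus-unreached table may stay if it is descriptive and labelled as reflecting reach, eligibility and consent together.

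The cost is revised wording, slightly more analysis, and a smaller logistic set if a wider one was intended: about ±10 points for a 30% trait at 150 vs 150, or about ±13 at 100 vs 100.
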